4.3 Criteria for Treatment through Progression of Disease and Retreatment

Patients with rapid tumour progression or with symptomatic progression that requires urgent medical intervention (eg, central nervous system metastasis, respiratory failure due to tumour compression, spinal cord compression) will not be eligible for continuing MEDI4736.

For all patients who completed the first 12 month period of treatment with MEDI4736 and had CR, PR, or SD at completion, retreatment during follow up would be offered on the basis of a patient having objective RECIST 1.1 disease progression with or without confirmation.

For all patients who are treated through progression, or patients who achieve disease control [ie, CR, PR, or SD] at 12 months and restart treatment upon evidence of PD during follow-up, the investigator should ensure patients do not have any significant, unacceptable or irreversible toxicities that indicate continuing or restarting treatment would not further benefit the patient. Patients who progressed during the first 12 months are not allowed re-treatment. In addition, the investigator should ensure patients meet the following inclusion criteria (criteria number from section 4.1):

- The patient must provide signed, written and dated retreatment or treatment through progression informed consent (criterion 1). These consent documents will specify that treatment beyond initial evidence of PD or re-treatment upon progression during follow up is not the standard of care and that alternative treatment options, either locally licensed treatments or other clinical trials, are available for this patient population.
- Meet serum creatinine CL >40 mL/min by the Cockcroft-Gault formula (or by 24-hour urine collection as defined by the formula in protocol inclusion criterion 11) and the criterion for AST/ALT.

The patient should not enter retreatment if any of the following exclusion criteria are fulfilled:

- Concurrent enrolment in another clinical study, unless it is an observational (non-interventional) clinical study or the follow-up period of an interventional study (criterion 4)
- Current or prior use of immunosuppressive medication within 28 days before the first dose of MEDI4736, with the exceptions of intranasal and inhaled corticosteroids or systemic corticosteroids at physiological doses, which are not to exceed 10 mg/day of prednisone, or an equivalent corticosteroid (criterion 8)
- Any unresolved toxicity CTCAE >Grade 2 from previous anti-cancer therapy. Patients with irreversible toxicity that is not reasonably expected to be exacerbated by the investigational product may be included (eg, hearing loss) after consultation with the AstraZeneca/MedImmune study physician (criterion 10)
- Any prior Grade ≥ 3 immune-related adverse event (irAE) while receiving any previous immunotherapy agent, or any unresolved irAE >Grade 1 (criterion 11)
- Be currently receiving, or have received in the interim period after stopping study drug, any chemotherapy, immunotherapy, biologic or hormonal therapy for cancer treatment. NOTE: Local treatment of isolated lesions, excluding target lesions, for palliative intent is acceptable (eg, by local surgery or radiotherapy) (criterion 12)
- Recent major surgery within 4 weeks prior to entry to retreatment (excluding the placement of vascular access) that would prevent administration of investigational product (criterion 14)

- Active or prior documented autoimmune disease within the past 2 years (patients with vitiligo, Grave's disease, or psoriasis not requiring systemic treatment within the past 2 years are not excluded) (criterion 15)
- Active or prior documented inflammatory bowel disease (eg, Crohn's disease, ulcerative colitis) (criterion 16)
- History of primary immunodeficiency (criterion 17)
- History of allogeneic organ transplant (criterion 18)
- History of hypersensitivity to MEDI4736 or any excipient (criterion 19)
- Brain metastases or spinal cord compression unless asymptomatic, treated and stable off steroids and anti-convulsants for at least 1 month prior to entry to retreatment (criterion 20)
- History of leptomeningeal carcinomatosis (criterion 21)
- Mean QT interval corrected for heart rate (QTc) ≥ 470 ms calculated from 3 electrocardiograms (ECGs) using Bazett's Correction (criterion 22)
- Uncontrolled intercurrent illness including, but not limited to, ongoing or active infection, symptomatic congestive heart failure, uncontrolled hypertension, unstable angina pectoris, cardiac arrhythmia, active peptic ulcer disease or gastritis, active bleeding diatheses including any patient known to have evidence of acute or chronic hepatitis B, hepatitis C or human immunodeficiency virus (HIV), or psychiatric illness/social situations that would limit compliance with study requirements or compromise the ability of the patient to give written informed consent (criterion 23)
- Active infection of tuberculosis, as determined by clinical signs and symptoms (criterion 24)
- Receipt of live attenuated vaccination within 30 days prior to retreatment or within 30 days of receiving MEDI4736 (criterion 25)
- Female patients who are pregnant, breast-feeding or male or female patients of reproductive potential who are not employing an effective method of birth control (criterion 27)
- Any condition that, in the opinion of the investigator, would interfere with evaluation of the investigational product or interpretation of patient safety or study results (criterion 28)

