13. Receipt of radiation therapy within 4 weeks prior to starting MEDI4736. Limited field of radiation for palliation within 2 weeks of the first dose of study treatment is allowed, provided:
 - The lung is not in the radiation field
 - Irradiated lesion(s) cannot be used as target lesions.
14. Recent major surgery within 4 weeks prior to entry into the study (excluding the placement of vascular access) that would prevent administration of investigational product
15. Active or prior documented autoimmune disease within the past 2 years. NOTE: Patients with vitiligo, Grave's disease, or psoriasis not requiring systemic treatment (within the past 2 years) are not excluded.
16. Active or prior documented inflammatory bowel disease (eg, Crohn's disease, ulcerative colitis)
17. History of primary immunodeficiency
18. History of allogeneic organ transplant
19. History of hypersensitivity to MEDI4736 or any excipient
20. Brain metastases or spinal cord compression unless asymptomatic, treated and stable off steroids and anti-convulsants for at least 1 month prior to entry into the study
21. History of leptomeningeal carcinomatosis
22. Mean QT interval corrected for heart rate (QTc) ≥ 470 ms calculated from 3 electrocardiograms (ECGs) using Bazett's Correction
23. Uncontrolled intercurrent illness including, but not limited to, ongoing or active infection, symptomatic congestive heart failure, uncontrolled hypertension, unstable angina pectoris, cardiac arrhythmia, active peptic ulcer disease or gastritis, active bleeding diatheses including any patient known to have evidence of acute or chronic hepatitis B, hepatitis C or human immunodeficiency virus (HIV), or psychiatric illness/social situations that would limit compliance with study requirements or compromise the ability of the patient to give written informed consent
24. Active infection of tuberculosis, as determined by clinical signs and symptoms

25. Receipt of live attenuated vaccination within 30 days prior to study entry or within 30 days of receiving MEDI4736
26. History of another primary malignancy except for:
 - Malignancy treated with curative intent and with no known active disease ≥ 5 years before the first dose of study drug and of low potential risk for recurrence
 - Adequately treated non-melanoma skin cancer or lentigo maligna without evidence of disease
 - Adequately treated carcinoma in situ without evidence of disease eg, cervical cancer in situ.

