5.5.2 Doses and treatment regimens

Patients enrolled in the study will receive 10 mg/kg via iv infusion Q2W ± 3 days. Treatment with MEDI4736 will commence on Day 1 following confirmation of eligibility and will

continue on a Q2W schedule for a maximum duration of treatment of 12 months (see [Table 1](#)). The final administration of MEDI4736 will be at the Week 50 visit. Treatment should be discontinued prior to 12 months if there is confirmed PD (unless the investigator considers the patient continues to receive benefit from treatment), initiation of alternative cancer therapy, unacceptable toxicity, withdrawal of consent, or other reasons to discontinue treatment occur.

Disease progression requires confirmation, treatment with MEDI4736 will continue between the initial assessment of progression and confirmation for progression.

If progression is not confirmed then the patient should continue on study treatment and on treatment assessments.

Patients who achieve and maintain disease control (ie, CR, PR, or SD) through to the end of the 12-month MEDI4736 treatment period will enter follow-up ([Table 2](#)). Upon evidence of PD following discontinuation of 12 months of treatment, patients may restart treatment with MEDI4736 for up to 12 months with the same treatment guidelines followed during the initial 12-month treatment period ([Table 1](#)). Patients will only be able to restart treatment once; thus a maximum of two 12-month periods will be allowed.

Patients who have a dose interruption due to toxicity at any point in the first 12 months of treatment may resume and complete the 12-month treatment period.

Patients who have confirmed PD during the 12-month initial treatment period or in the 12-month period after restarting MEDI4736 and cannot continue to receive MEDI4736 will enter follow-up with assessments as shown in [Table 3](#).

Patients with PD that continue to receive MEDI4736 at the discretion of the investigator (following consultation with the sponsor) can receive treatment for a maximum of 12 months (and will follow the assessments in [Table 1](#) including tumour assessments).

Study drug should be discontinued if there is confirmed PD following a previous response (PR or CR) to study drug.

5.5.2.1 **MEDI4736 treatment administration**

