Patients who achieve and maintain disease control (ie, CR, PR, or SD) through to the end of the 12-month MEDI4736 treatment period may restart treatment with MEDI4736 upon evidence of PD, with or without confirmation, during follow-up. To restart treatment the patient must not have received an intervening systemic anti-cancer therapy post-MEDI4736 discontinuation. Patients who restart MEDI4736 must have a baseline tumour assessment within 28 days of restarting treatment with MEDI4736, all further scans should occur every 8 weeks (relative to the date of restarting treatment) until study treatment is stopped (maximum of 12 months of further treatment).

It is important to follow the assessment schedule as closely as possible. Please refer to the study plans ([Table 1](#) [Screening and the Treatment Period], [Table 2](#) [for follow-up of patients achieving disease control or who are discontinued due to toxicity in the absence of confirmed PD] and [Table 3](#) [for follow-up of patients discontinuing due to confirmed PD]) and [Appendix F](#).

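### The retreatment version of exclusion criterion 8 still counts its 28 days back from the original first dose, so as worded it requires no immunosuppressant washout before a restart

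*Protocol*

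**What the plan says.** Patients who complete the first 12-month course with disease control, and who later progress in follow-up, may restart MEDI4736 once. Section 4.3 gives the exclusions that apply at that point, each cross-referenced to its number in Section 4.2.

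Criterion 8 in the Section 4.3 list reads "Current or prior use of immunosuppressive medication within 28 days before the first dose of MEDI4736", followed by the exceptions for intranasal and inhaled steroids and for systemic steroids up to 10 mg/day prednisone equivalent. The entry criterion in Section 4.2 has the same wording and the same reference date.

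Three other criteria in the list also carry a look-back that, in Section 4.2, ran from study entry:

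- **Criterion 14.** Section 4.2 has "Recent major surgery within 4 weeks prior to entry into the study"; Section 4.3 has "Recent major surgery within 4 weeks prior to entry to retreatment".
- **Criterion 20.** The period off steroids and anti-convulsants ran to study entry in Section 4.2; in Section 4.3 it is "for at least 1 month prior to entry to retreatment".
- **Criterion 25.** Section 4.2 has "Receipt of live attenuated vaccination within 30 days prior to study entry"; Section 4.3 has "Receipt of live attenuated vaccination within 30 days prior to retreatment".

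Elsewhere the protocol names the restart date when it means it. Section 6.3.1 says that patients who restart "must have a baseline tumour assessment within 28 days of restarting treatment with MEDI4736".

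**The concern.** A retreatment exclusion should test the patient's state at restart. Criterion 8 has two limbs, current use and prior use within 28 days. The current-use limb works at restart. The prior-use limb, taken as written, looks at a period that ended about a year earlier and that the patient already had to pass to receive the first dose.

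The evident purpose is a 28-day washout before the second course, and the words do not require one. A patient on systemic steroids above 10 mg/day prednisone equivalent until two weeks before restart is not excluded by the literal text. There is a plausible route to this. Appendix G directs prednisone 1–2 mg/kg/day for persistent Grade 2 immune-related events. Once such an event has resolved, criterion 11 no longer excludes the patient.

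Section 4 allows no exceptions to the eligibility criteria, so the wording matters. Two sites could decide differently on the same patient, and each could cite the protocol.

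**Working it through.** The protocol gives no figure to reproduce here. The check compares the wording and then the dates.

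**Reference dates**

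| Criterion | Section 4.2 (entry) counts from | Section 4.3 (retreatment) counts from | Re-dated? |
|---|---|---|---|
| 8, immunosuppressants, 28 days | first dose of MEDI4736 | first dose of MEDI4736 | no |
| 14, major surgery, 4 weeks | entry into the study | entry to retreatment | yes |
| 20, off steroids and anti-convulsants, 1 month | entry into the study | entry to retreatment | yes |
| 25, live vaccine, 30 days | study entry | retreatment | yes |

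Three of the four were re-dated. Criterion 12 was also reworded, to cover cancer therapy received after stopping study drug.

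**Dates**

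Inputs:

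- The first dose is on Day 1, Week 0 (Table 1).
- "The final administration of MEDI4736 will be at the Week 50 visit" (Section 5.5.2).
- The dosing window is ±3 days (Section 5.5.2).
- Retreatment follows completion of the first course (Section 4.3).

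Steps:

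1. Literal window: the 28 days before Day 1.
2. Last first-course dose: 1 + 50 × 7 = Day 351, which is 350 days after the first dose. With the −3-day window it is Day 348, or 347 days after.
3. A restart comes after the last first-course dose, so using that dose day as the restart day is a conservative bound. The 28 days before it open at 351 − 28 = Day 323, or 348 − 28 = Day 320 with the dosing window.
4. The literal window closes before Day 1 and the window of interest opens no earlier than Day 320. Overlap: 0 of 28 days.

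**Does another rule supply the washout?**

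- Section 5.6 restricts immunosuppressants given alongside study treatment and sets no look-back before a restart.
- Criterion 11 concerns the grade and resolution of immune-related events, not the drugs used to treat them.
- The steroid condition in criterion 20 applies only to brain metastases or spinal cord compression.
- Criterion 28 is investigator judgement.

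None of these is a general 28-day washout.

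**The case against.** The best defence is context. The list is introduced as governing entry to retreatment, so the first dose can be read as the first dose of that course. On the literal reading the prior-use limb does nothing, which is a reason to prefer the sensible one. Criteria 14, 20 and 25 referred to study entry, a term that cannot describe a restart and so had to change. Criterion 8 referred to a first dose, which could be carried over. The retreatment note to Table 1 also repeats the screening assessments, and the screening column covers Days −28 to −1 and includes concomitant medication. A site following that schedule would review medication in roughly the right period.

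The practical stake can be questioned too. For many Grade 2 immune-mediated events, Appendix G lets dosing resume 5–7 days after a steroid taper is completed. The protocol therefore already accepts dosing well inside 28 days of steroid use.

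Much of this stands. The intended reading is clear enough that many sites will apply it, and no specific harm from a shorter gap has been shown. But recording a medication does not make it an exclusion. The Appendix G rule governs doses held within a course; it does not replace an eligibility washout that the sponsor chose to carry into Section 4.3. The protocol also distinguishes the first infusion from the date of restarting treatment elsewhere, so first dose is not its usual term for the restart dose. The objection reduces the consequence but does not correct the text.

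**Conclusion.** The point holds as a minor error of wording in an operative eligibility rule. As written, the prior-use part of criterion 8 has no effect at restart: its window overlaps the 28 days before any restart by 0 of 28 days. Immunosuppression that ended 1 to 28 days before restart is therefore not excluded, while current use still is.

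This rests on reading the first dose as the original Day 1. If a site reads it as the first retreatment dose, the criterion works as intended.

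The effect is confined to eligibility for the optional second course. The number of patients concerned cannot be derived from the protocol and is probably small. The primary response-rate analysis is unaffected, because Section 11.1.3 uses data only up to progression, and the sample size does not change.

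**What to change.** In the Section 4.3 bullet for criterion 8, change the end of the time phrase to *within 28 days before the first dose of MEDI4736 retreatment*, in line with criteria 14, 20 and 25. The Section 4.2 criterion stays as it is.

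The cost is one phrase in the next amendment. Concomitant medication is already among the screening assessments repeated for retreated patients, so there is no new data collection and no change to any analysis.

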5. STUDY CONDUCT

5.1 Restrictions during the study

1. Females of childbearing potential who are sexually active with a nonsterilised male partner must use 2 methods of effective contraception from screening, and must agree to continue using such precautions for 90 days after the final dose of investigational product; cessation of birth control after this point should be discussed with a responsible physician. Periodic abstinence, the rhythm method, and the withdrawal method are not acceptable methods of birth control.
 - Females of childbearing potential are defined as those who are not surgically sterile (ie, bilateral tubal ligation, bilateral oophorectomy, or complete hysterectomy) or postmenopausal (defined as 12 months with no menses without an alternative medical cause).
 - Patients must use 2 acceptable methods of effective contraception as described in Table 4.
2. Nonsterilised males who are sexually active with a female partner of childbearing potential must use 2 acceptable methods of effective contraception (see Table 4) from Day 1 and for 90 days after receipt of the final dose of investigational product.

Table 4 Effective methods of contraception (two methods must be used)

Barrier Methods	Intrauterine Device Methods	Hormonal Methods
Male condom plus spermicide	Copper T	Implants
Cap plus spermicide	Progesterone T ^a	Hormone shot or injection
Diaphragm plus spermicide	Levonorgestrel-releasing intrauterine system (eg, Mirena [®]) ^a	Combined pill Minipill Patch

^a This is also considered a hormonal method.

3. Patients should not donate blood whilst participating in this study
4. During the study patients may receive palliative radiotherapy at the site of bone metastases that were present at baseline, providing the investigator does not feel that the bone pain is indicative of clinical disease progression. If a patient has further bone pain for which a second course of palliative radiation therapy is considered, the patient should be discussed with the study physician to decide if it is necessary for a patient to be discontinued from study therapy. The need for radiotherapy to any other site should be discussed with the study physician and any decisions will be made on a case-by-case basis.

Restrictions relating to concomitant medications are described in Section 5.6.

5.2 Patient enrolment

At Pre-screening, the Principal Investigator, or suitably trained delegate, will:

1. Obtain signed informed consent (main study) from the potential patient before any study specific procedures are performed.
2. Assign potential patient a unique 7-digit enrolment number, beginning with 'E#'. The Enrolment Code is assigned to each patient as an identifier. This is obtained through the Interactive Voice Response System (IVRS)/Interactive Web Response System (IWRS) (ECCNNXXX: CC being the country code. NN being the centre number, XXX being the patient enrolment code at the centre). Enrolment codes will start at 001 in each centre and go up sequentially (eg, at Centre 01, patients will be assigned E codes E0101001, E0101002 etc)
3. Determine preliminary patient eligibility (investigator's opinion).
4. Send patient's tumour sample for pre-screening PD-L1 status.

At Screening, the Principal Investigator, or suitably trained delegate, will:

5. Determine formal patient eligibility (see Sections 4.1 and 4.2).

At Day 1 (Baseline), once the patient is confirmed to be eligible, the Principal Investigator, or suitably trained delegate, will:

6. Call IVRS/IWRS for kit assignment.

Patients may be enrolled but not treated. If the patient is not treated, the IVRS/IWRS should be contacted to terminate the patient in the system.

The IVRS/IWRS will be used to track drug supply.

If a patient withdraws from participation in the study, then his/her enrolment code cannot be reused and they cannot re-enter into the study.

All patients entering the study should have known *EGFR* TK mutation or *ALK* fusion status to ensure patients are assigned to the appropriate cohort. Recruitment into Cohort 3 will only start once recruitment into Cohort 2 is complete.

The study is designed to accrue at least 188 PD-L1 positive patients (94 patients with $\geq 25\%$ of tumours with membrane staining for each of Cohorts 1 and 2) and, in addition, at least 94 PD-L1 positive patients with $\geq 90\%$ of tumour cells with membrane staining for Cohort 3. However, due to the lag time associated with determination of PD-L1 status relative to dosing, there will be over-recruitment into any cohort.

In the event that no valid test result is available, eligible patients with unknown *EGFR* TK mutation or *ALK* fusion status will be enrolled into the *EGFR/ALK* wild type cohorts.

The IVRS/IWRS may not be available at the start of the study. In this event a manual process will need to be followed.

5.3 Procedures for handling patients incorrectly enrolled or initiated on investigational product

Patients who fail to meet the inclusion/exclusion criteria should not, under any circumstances, be enrolled or receive study medication. There can be no exceptions to this rule.

Where patients that do not meet the inclusion and/or exclusion criteria, are enrolled in error, or are incorrectly started on treatment, or where patients subsequently fail to meet the study criteria post initiation, a discussion must occur between the study physician and the investigator regarding the patient's safety and well-being and whether to continue or discontinue the patient from the investigational product.

The study physician is to ensure all such contacts are appropriately documented. In situations where an agreement cannot be reached, the patient should have their study therapy stopped, then enter follow-up where possible as per Section 5.8.

